5.9 Nonserious Adverse Event

- Nonserious Adverse Events are to be provided to BMS in aggregate via interim or final study reports as specified in the agreement or, if a regulatory requirement [e.g. IND US trial] as part of an annual reporting requirement.
- The collection of nonserious AE information should begin at initiation of study drug. All nonserious adverse events (not only those deemed to be treatment-related) should be collected continuously during the treatment period and for a minimum of 100 days following the last dose of study treatment.

- Nonserious AEs should be followed to resolution or stabilization, or reported as SAEs if they become serious. Follow-up is also required for nonserious AEs that cause interruption or discontinuation of study drug and for those present at the end of study treatment as appropriate.

5.10 Laboratory Test Abnormalities

- All laboratory test results captured as part of the study should be recorded following institutional procedures. Test results that constitute SAEs should be documented and reported as such.
- The following laboratory abnormalities should be documented and reported appropriately:
 - any laboratory test result that is clinically significant or meets the definition of an SAE
 - any laboratory abnormality that required the subject to have study drug discontinued or interrupted
 - any laboratory abnormality that required the subject to receive specific corrective therapy.

5.11 Pregnancy

- Any pregnancy that occurs in a female partner of a male study participant should be reported to BMS. Information on this pregnancy will be collected on the Pregnancy Surveillance Form.

5.12 Overdose

- An overdose is defined as the accidental or intentional administration of any dose of a product that is considered both excessive and medically important. All occurrences of overdose must be reported as an SAE.

5.13 Other Safety Considerations

- Any significant worsening noted during interim or final physical examinations, electrocardiograms, x rays, and any other potential safety assessments, whether or not these procedures are required by the protocol, should also be recorded as a nonserious or serious AE, as appropriate, and reported accordingly.

5.14 Seven Calendar-Day Telephone or Fax Report:

The IND Sponsor is required to notify the FDA of any fatal or life-threatening adverse event that is unexpected and assessed by the investigator to be possibly related to the investigational agent. Such reports are to be telephoned or faxed [contact]) to the FDA within seven calendar days of first learning of the event. Follow-up information will be submitted to the FDA as soon as relevant information is available.

5.15 15 Calendar-Day Written Report:

The IND Sponsor is required to notify the FDA of any SAE that is unexpected and related to the investigational agent in a written IND Safety Report.

Written IND Safety Reports should include an Analysis of Similar Events in accordance with regulation 21 CFR § 312.32. All safety reports previously filed with the IND concerning similar events should be analyzed. The new report should contain comments on the significance of the new event in light of the previous related reports.

Written IND safety reports with Analysis of Similar Events are to be submitted to the FDA within 15 calendar days of first learning of the event. Follow-up information will be submitted to the FDA as soon as relevant information is available.

SAEs should be reported on MedWatch Form 3500A, which can be accessed at: <http://www.accessdata.fda.gov/scripts/medwatch/>.

Harold C. Simmons
Comprehensive Cancer Center

MedWatch SAE forms should be sent to the FDA at:

MEDWATCH

[name]

[name]

Fax: [name] ([name])

<http://www.accessdata.fda.gov/scripts/medwatch/>

All SAEs should simultaneously be faxed or e-mailed to BMS at:

Global Pharmacovigilance & Epidemiology

Bristol-Myers Squibb Company

[contact]

Email: [contact]

Following the subject's written consent to participate in the study, all SAEs, whether related or not related to study drug, must be collected, including those thought to be associated with protocol-specified procedures. All SAEs must be collected that occur within 100 days of discontinuation of dosing.

All SAEs must be collected that occur during the screening period. If applicable, SAEs must be collected that relate to any protocol-specified procedure (eg, a follow-up skin biopsy). The investigator should report any SAE that occurs after these time periods that is believed to be related to study drug or protocol-specified procedure.

SAEs, whether related or not related to study drug, and pregnancies must be reported to BMS within 24 hours. SAEs must be recorded on BMS or an approved form; pregnancies must be recorded on a Pregnancy Surveillance Form.

SAE Email Address: [contact]

SAE [contact]

If only limited information is initially available, follow-up reports are required. (Note: Follow-up SAE reports should include the same investigator term(s) initially reported.) If an ongoing SAE changes in its intensity or relationship to study drug or if new information becomes available, a follow-up SAE report should be sent within 24 hours

to the BMS (or designee) using the same procedure used for transmitting the initial SAE report. All SAEs should be followed to resolution or stabilization.

The Sponsor/Investigator will ensure that all SAEs in the clinical database are reported to BMS and any applicable health authority during the conduct of the study. This reconciliation will occur at least quarterly and be initiated by the sponsor/investigator.

Sponsor/investigator will request a reconciliation report from: [contact]. During reconciliation, any events found to not be reported previously to BMS must be sent to [contact].

6 ETHICAL CONSIDERATIONS

6.1 Good Clinical Practice

This study will be conducted in accordance with Good Clinical Practice (GCP), as defined by the International Conference on Harmonisation (ICH) and in accordance with the ethical principles underlying European Union Directive 2001/20/EC and the United States Code of Federal Regulations, Title 21, Part 50 (21CFR50).

The study will be conducted in compliance with the protocol. The protocol and any amendments and the subject informed consent will receive Institutional Review Board/Independent Ethics Committee (IRB/IEC) approval/favorable opinion prior to initiation of the study.

All potential serious breaches must be reported to Principal Investigator ([name]). A serious breach is a breach of the conditions and principles of GCP in connection with the study or the protocol, which is likely to affect, to a significant degree, the safety or physical or mental integrity of the subjects of the study or the scientific value of the study.

Personnel involved in conducting this study will be qualified by education, training, and experience to perform their respective tasks. This study will not use the services of study personnel where sanctions have been invoked or where there has been scientific misconduct or fraud (eg, loss of medical licensure, debarment).

6.2 Institutional Review Board/Independent Ethics Committee

Before study initiation, the investigator must have written and dated approval/favorable opinion from the IRB/IEC for the protocol, consent form, subject recruitment materials (eg, advertisements), and any other written information to be provided to subjects. The principal investigator should also provide the IRB/IEC with a copy of the Investigator Brochure or product labeling information to be provided to subjects and any updates. The principal investigator should provide the IRB/IEC with reports, updates and other information (eg, expedited safety reports, amendments, and administrative letters) according to regulatory requirements or institution procedures.

6.3 Informed Consent

Investigators must ensure that subjects are clearly and fully informed about the purpose, potential risks, and other critical issues regarding clinical studies in which they volunteer to participate.

In situations where consent cannot be given to subjects, their legally acceptable representatives are clearly and fully informed about the purpose, potential risks, and other critical issues regarding clinical studies in which the subject volunteers to participate.

The informed consent form will include all elements required by Registration of Pharmaceuticals for Human Use (ICH), Good Clinical Practice (GCP) and applicable regulatory requirements and will adhere to the ethical principles that have their origin in the Declaration of Helsinki.

Investigators must:

1. Provide a copy of the consent form and written information about the study in the language in which the subject is most proficient prior to clinical study participation. The language must be non-technical and easily understood.
2. Allow time necessary for subject or subject's legally acceptable representative to inquire about the details of the study.
3. Obtain an informed consent signed and personally dated by the subject or the subject's legally acceptable representative and by the person who conducted the informed consent discussion.

4. Obtain the IRB/IEC's written approval/favorable opinion of the written informed consent form and any other information to be provided to the subjects, prior to the beginning of the study, and after any revisions are completed for new information.
5. If informed consent is initially given by a subject's legally acceptable representative or legal guardian, and the subject subsequently becomes capable of making and communicating his or her informed consent during the study, consent must additionally be obtained from the subject.
6. Revise the informed consent whenever important new information becomes available that is relevant to the subject's consent. The investigator, or a person designated by the investigator, should fully inform the subject or the subject's legally acceptable representative or legal guardian, of all pertinent aspects of the study and of any new information relevant to the subject's willingness to continue participation in the study. This communication should be documented.

The confidentiality of records that could identify subjects must be protected, respecting the privacy and confidentiality rules applicable to regulatory requirements, the subjects' signed ICF and, in the US, the subjects' signed HIPAA Authorization.

The consent form must also include a statement that investigators and regulatory authorities have direct access to subject records. The rights, safety, and well-being of the study subjects are the most important considerations and should prevail over interests of science and society.

6.4 Multicenter Guidelines

The Protocol Chair

The Protocol Chair, [name] PhD, is responsible for performing the following Tasks:

- Coordinating, developing, submitting, and obtaining approval for the protocol as well as its subsequent amendments
- Assuring that all participating institutions are using the current IRB approved version of the protocol
- Taking responsibility for the overall conduct of the study at all participating institutions and for monitoring the progress of the study
- Reviewing and ensuring reporting of Serious Adverse Events (SAEs)

from all sites

- Reviewing all study data from all sites

6.5 Coordinating Center Responsibilities (UTSW)

Coordinating Centers must:

- Verify that each participating institution has a Federal Wide Assurance (FWA) number.
- Confirm that IRB approval has been obtained at each participating site prior to their first patient registration
- Maintain copies of IRB approvals from each site
- Implement central patient registration
- Prepare all submitted data for review by the Protocol Chair ([name] PhD)
- Establish procedures for documentation, reporting, and submitting of adverse events to the Protocol Chair ([name] PhD) and all applicable parties
- Facilitate audits by securing selected source documents and research records from participating sites for audit, or by conducting audits at participating sites.

6.6 Participating Sites Responsibilities

Participating sites are responsible for performing the following tasks:

6.6.1 Follow the protocol as written and conduct the study within the guidelines of Good Clinical Practice

6.6.2 Required Documentation (for multi-site studies)

Before the study can be initiated at any site, the following documentation must be provided to the Department of Urology {Research Office}.

- A copy of the official IRB approval letter for the protocol and informed consent
- IRB membership list or Federal wide Assurance letter
- CVs and medical licensure for the principal investigator and any associate investigators who will be involved in the study
- Form FDA 1572 appropriately filled out and signed with appropriate documentation (NOTE: this is required if {institution} holds the IND. Otherwise, the affiliate Investigator's signature on the protocol is sufficient to ensure compliance)
- A copy of the IRB-approved consent form
- CAP and CLIA Laboratory certification numbers and institution lab normal values
- Executed clinical research contract

7 Data Management, Monitoring/Auditing and Reporting Requirements

REDCap is the UTSW SCC institutional choice for the electronic data capture of case report forms for SCC Investigator Initiated Trials. REDCap will be used for electronic case report forms in accordance with Simmons Cancer Center requirements as appropriate for the project. In order to facilitate remote source to case report form verification, the Simmons Comprehensive Cancer Center study team will require other institutions participating in this trial as sub-sites to enter data into the selected EDC system and upload selected de-identified source materials when instructed.

Trial monitoring will be conducted no less than annually and refers to a regular interval review of trial related activity and documentation performed by the DOT, and/or the CRO Multi-Center IIT Monitor. This review includes but is not limited to accuracy of case report forms, protocol compliance, timeliness and accuracy of Velos entries and AE/SAE management and reporting. Documentation of trial monitoring will be maintained along with other protocol related documents and will be reviewed during internal audit.

For further information, refer to the UTSW SCCC IIT Management manual.

Toxicity reviews will be performed after the first 6 patients have been enrolled and then on a quarterly basis. These reviews will be documented in the form of short summaries after investigator discussions. The principle investigators of all accruing STU072016-044, [name], FormA-ResearchProtocol-V7.0-09.30.19, Mod_14, 10-23-19 (2)

Page 79 of 99 (BMS CA209-444) V. V6.0 date March 1, 2019

This material is the property of the [UTSW Simmons Cancer Center](#). Do not disclose or use except as authorized in writing by the study sponsor.

sites are required to participate. The UTSW Simmons Cancer Center (SCC) Data Safety Monitoring Committee (DSMC) is responsible for monitoring data quality and patient safety for all UTSW SCC clinical trials. As part of that responsibility, the DSMC reviews all local serious adverse events and unanticipated problems in real time as they are reported and reviews adverse events on a quarterly basis. The quality assurance activity for the Clinical Research Office provides for periodic auditing of clinical research documents to ensure data integrity and regulatory compliance. A copy of the DSMC plan is available upon request.

The SCC DSMC meets quarterly and conducts annual comprehensive reviews of ongoing clinical trials, for which it serves as the DSMC of record. The QAC works as part of the DSMC to conduct regular audits based on the level of risk. Audit findings are reviewed at the next available DSMC meeting. In this way, frequency of DSMC monitoring is dependent upon the level of risk. Risk level is determined by the DSMC Chairman and a number of factors such as the phase of the study; the type of investigational agent, device or intervention being studied; and monitoring required to ensure the safety of study subjects based on the associated risks of the study. Protocol-specific DSMC plans must be consistent with these principles.

8 STUDY MANAGEMENT

8.1 Adherence to the Protocol

Except for an emergency situation in which proper care for the protection, safety, and well-being of the study subject requires alternative treatment, the study shall be conducted exactly as described in the approved protocol.

8.2 Emergency Exceptions(also called single-subject exceptions or single-subject waivers)

These include any departure from IRB-approved research that is *not due to an emergency* and is:

- intentional on part of the investigator; or
- in the investigator's control; or
- not intended as a systemic change (e.g., single-subject exceptions to eligibility [inclusion/exclusion] criteria)

➤ **Reporting requirement:** Exceptions are non-emergency deviations that require **prospective** IRB approval before being implemented. Call the IRB if your request is urgent. If IRB approval is not obtained beforehand, this constitutes a major deviation.

Emergency Deviations: include any departure from IRB-approved research that is necessary to:

- avoid immediate apparent harm, or
- protect the life or physical well-being of subjects or others

Reporting requirement: Emergency deviations must be promptly reported to the IRB within (5) working days of the occurrence.

8.3 Major Deviations/ (also called violations): include any departure from IRB-approved research that:

- Harmed or placed subjects(s) or others at risk of harm (e., did or has the potential to negatively affect the safety, rights or welfare of subjects or others), or
- Affect data quality (e.g., the completeness, accuracy, reliability, or validity of the data) or the science of the research (e.g., the primary outcome/endpoint of the study)
 - **Reporting requirement:** Major deviations must be promptly reported to the IRB within 5 working days of PI awareness.

8.3.1 Minor Deviations: include any departure from the IRB approved research that:

- Did not harm or place subjects(s) or others at risk of harm (i.e., did not or did not have the potential to negatively affect the safety, rights, or welfare of subjects or others), or
 - Did not affect data quality (e.g., the completeness, accuracy, reliability, or validity of the data) or the science of the research (e.g., the primary outcome/endpoint of the study)

➤ **Reporting requirement:** Major deviations must be promptly reported to the IRB within 5 working days of PI awareness.

- Harmed or placed subject(s) or Others at risk of harm (i.e., did or has the potential to negatively affect the safety, rights, or welfare of subjects or others), or
- Affect data quality (e.g., the completeness, accuracy, reliability, or validity of the data) or the science of the research (e.g., the primary outcome/endpoint of the study)

➤ **Reporting requirement:** Major deviations must be promptly reported to the IRB within 5 working days of PI awareness.

8.4 Amendments to the Protocol

Should amendments to the protocol be required, the amendments will be originated and documented by the Principal Investigator. A summary of changes document outlining proposed changes as well as rationale for changes, when appropriate, is highly recommended. When an amendment to the protocol substantially alters the study design or the potential risk to the patient, a revised consent form might be required.

8.5 Case Report Form Submission

Data required by the study will be collected in Case Report Forms provided by the Coordinating Center (SKCCC). The participating site will be required to complete a paper Eligibility Checklist case report form (CRF) at the time of patient registration. All other data will be collected on the electronic case report forms (eCRFs) in CRMS. Site staff access to CRMS will be initiated at the time of the site activation.

8.5.1 Case Report Forms

Case report forms (e-CRF) will be generated by Staff at the Lead Site Coordinating Center at UTSW for the collection of all study data. Investigators will be responsible for ensuring that the CRFs are kept up-to-date.

8.5.2 Case Report Form Completion

The paper Eligibility Checklist CRF must be completed using black ink. Any errors must be crossed out so that the original entry is still visible, the correction clearly indicated and then initialed and dated by the individual making the correction.

eCRFs(REDCAP) will be completed within 2 weeks of the patient coming to the clinic and all relevant supporting documentation such as scans, progress notes, nursing notes, blood work, pathology reports, etc., will be submitted to the Coordinating Center (UTSW) via email at [contact] to the Lead Center Program Coordinator, [name]. All patient names or other identifying information will be removed prior to being sent to the Coordinating Center (UTSW) or non- redacted source documents can be sent via a password -protected/ secured document transfer based on each institution's guidelines.

Authorized representatives of the Coordinating Center (UTSW) may be performing audits or inspections, including source data verification. The purpose of these audits or inspections is to systematically and independently examine all trial-related activities and documents to determine whether these activities were conducted and data were recorded, analyzed, and accurately reported according to the protocol, Good Clinical Practice (GCP), and any applicable regulatory requirements.

9 Statistical Considerations

9.1 Study Design

This is a multi-institution, open-label, single-arm Phase II study to determine the safety and efficacy of SBRT followed by nivolumab in combination with ipilimumab in patients with metastatic RCC. The primary endpoints of safety evaluated by the level of G3/4 treatment related adverse events and the need for corticosteroids in this patient population and ORR assessed by RECIST criteria. Secondary endpoints include TTP, DOR, PFS, OS and local control of irradiated lesion. Simon's minimax two-stage design will be used to allow for early termination of the study if addition of SBRT to nivolumab in combination with ipilimumab is unlikely to be promising. A safety run-in phase will be included in the first 6 patients, and safety will be monitored continuously after this safety run-in phase using a Bayesian posterior probability approach.

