2.1 Study Design

This is a multi-institution, single-arm phase II study to determine the safety and efficacy of SBRT (up to 2 metastatic sites preferentially lung, mediastinum or bone in combination of nivolumab and ipilimumab in patients with metastatic RCC (with a clear-cell component and at least 1 measurable metastatic lesion that is not being irradiated). The primary endpoints are safety and tolerability as well as ORR of the combination of nivolumab plus ipilimumab with SBRT.

The study is planned based on a two-stage design that allows early termination for lack of efficacy. A safety run-in phase will be included comprising the first 6 patients at minimum to ensure that the combination of nivolumab plus ipilimumab and SBRT is safe. Then, we will determine whether the combination of nivolumab plus ipilimumab and SBRT yields a clinically compelling antitumor activity measured as ORR, and evaluate other endpoints including TTP, DOR, PFS, OS and local control of irradiated sites.

Safety Run-in phase

There is no previous experience with SBRT used concurrently with nivolumab and ipilimumab in this study population. **Therefore, to ensure that the combination is safe, the first six patients will be treated and observed for toxicity for 6 weeks after radiation before continuing with further accrual.** Therefore, six patients will be enrolled at the proposed dose of nivolumab and ipilimumab in combination with SBRT. If 4 out of the first 6 patients experience Grade 3/4 toxicity or a lower grade toxicity requiring immune suppressive therapy during the safety run-in observation period (6 weeks after completion of SBRT), enrollment will cease and the study will be halted until further safety analysis of the combination regimen can be performed. If less than 4 out of the first 6 patients experience Grade 3/4 toxicities or require steroids, we will proceed with additional accrual with this regimen.

Toxicity Event: \geq grade 3 adverse event (CTCAE v 4.0) with an attribution of possible, probable, or definite, as well as need for steroids/ immunosuppressive therapy and lower grade toxicity

Efficacy phase:

A minimax Simon two-stage design is planned with the maximum sample size of 25 (including the 6 in the safety run-in phase). A total of 15 patients will be entered in the first

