9.3 Justification for the Sample Size

The point estimate of the ORR with nivolumab in combination with ipilimumab in this patient population is 40%, based on the Phase I presented at ASCO meeting which is chosen as the reference rate (P0) in the study proposed. The response rate where the regimen would be considered promising to pursue further is 70% (P1). In the first stage,

responses will be evaluated on the first 15 subjects treated. If 6 or fewer responses are observed after 6-18 weeks of follow-up, the study will be terminated for futility. Otherwise, 10 additional subjects will be accrued to target a total of 25 treated subjects. During the evaluation of response in the first stage, we will continue the recruitment and treatment of subjects. This design has at least a 90% chance (power) of concluding the combination therapy is effective when the true response rate is 70% and a 5% chance (Type I error) of concluding the treatment is effective when the true response rate is 40% or less. The probability of stopping early is 61% if the true response rate is 40% or less and 1.5% if the true response rate is 70%. The null hypothesis will be rejected and the regimen will be declared a success if at the end of the study 17 or more responses are observed in 25 treated subjects. The anticipated accrual rate for this group of patients is expected to be 2 patients per month.

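### The 15/25 design is labelled Simon minimax but is not, and its stated 5% type I error and 90% power do not fit the written success rule of 17 or more out of 25

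*Combined protocol and SAP*

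**What the plan says.** Two sections name the design. Section 9.1: "Simon's minimax two-stage design will be used to allow for early termination of the study". Section 2.1: "A minimax Simon two-stage design is planned with the maximum sample size of 25".

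Section 9.3 gives the inputs and the rule. The reference rate P0 is 40% and the rate of interest P1 is 70%. For stage 1, "responses will be evaluated on the first 15 subjects treated", and "If 6 or fewer responses are observed after 6-18 weeks of follow-up, the study will be terminated for futility". Otherwise 10 more are treated, for 25 in all, and the regimen succeeds with 17 or more responses. Section 2.1 gives the same cut-off of 17.

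The claimed properties, also in 9.3, are power of at least 90% at a true rate of 70%, "a 5% chance (Type I error) of concluding the treatment is effective when the true response rate is 40% or less", and early-stopping probabilities of 61% at P0 and 1.5% at P1.

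The two sections differ on the futility stop. Section 9.3 terminates the study at 6 or fewer responses. Section 2.1 has termination discussed after a review of the data, and lets the team go on accruing if some patients show shrinkage or come close to a partial response.

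**The concern.** Minimax has a fixed meaning: among two-stage designs that meet the type I error and power limits, it is the one with the smallest maximum sample size, with ties broken by expected size under the null. Section 9.3 gives every input needed to test the label, and a reader who enters them into a standard Simon calculation does not get 15/25.

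The more consequential mismatch shows up in the same check. The error rates in 9.3 are the basis for 25 patients and for any claim that the regimen is promising. If they describe a cut-off other than the written one, the trial has a different chance of recognising an active regimen from the one its readers and approvers were told.

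**Working it through.** **Inputs.** P0 = 0.40, P1 = 0.70, type I error limit 0.05, power limit 0.90, stage 1 n1 = 15 with r1 = 6, total n = 25, success at s = 17 or more (all in 9.3; the label is in 2.1 and 9.1).

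**Formulas** (exact binomial)
- Early stop: PET(p) = P(X1 ≤ r1), with X1 ~ Bin(n1, p).
- Success with a binding stop: sum over x from r1 + 1 to n1 of P(X1 = x) × P(X2 ≥ s − x), with X2 ~ Bin(n − n1, p).
- Expected size: n1 + (n − n1) × (1 − PET).

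**Step 1: the plan's early-stopping figures.** P(X1 ≤ 6) with n1 = 15 is 0.610 at p = 0.40 and 0.015 at p = 0.70. Both match 9.3, so the stage 1 rule has been read as intended.

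**Step 2: error rates of the 15/25 design by final cut-off, stopping at 6 or fewer of 15.**

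| Success at | Type I error (p = 0.40) | Power (p = 0.70) |
|---|---|---|
| ≥14/25 | 7.5% | 95.1% |
| ≥15/25 | 3.4% | 90.0% |
| ≥16/25 | 1.3% | 81.0% |
| ≥17/25 (as written) | 0.43% | 67.7% |

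No cut-off gives exactly 5%. Only ≥15 satisfies both limits. The written cut-off falls short of the stated power by 90 − 67.7 = 22.3 percentage points.

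**Step 3: is 15/25 minimax for the stated inputs?** All combinations of n1, r1, n and s were searched for type I error ≤ 0.05 and power ≥ 0.90 with a binding stop.
- n ≤ 23: no feasible design.
- n = 24: five feasible designs, all with success at ≥14. The smallest expected size under P0 belongs to stop at ≤4/10, success at ≥14/24: type I error 4.82%, power 90.1%, PET 63.3% at P0 and 4.7% at P1, expected size 10 + 14 × (1 − 0.633) = 15.1.
- n = 25: the best is stop at ≤6/15, success at ≥15/25, with expected size 15 + 10 × (1 − 0.610) = 18.9.

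The minimax design is therefore 10/24. The 15/25 design with a cut-off of 15 is the best at n = 25, one patient above the minimum.

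**Step 4: if the stop can be overridden, as 2.1 allows.** Type I error must then be computed without credit for stopping, as P(Bin(n, 0.40) ≥ s).
- ≥14/24: 5.35%, above the limit. This applies to all five n = 24 designs.
- ≥15/25: 3.44%, against 3.40% with a binding stop.
- ≥17/25: 0.43%, unchanged. With 6 or fewer responses in stage 1, at most 6 + 10 = 16 are possible, so the stop cannot affect this rule.

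The conflict between 2.1 and 9.3 over the stop therefore does not explain the mismatch in Step 2.

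**The case against.** The strongest defence of the label is that it fails only if the futility stop is binding. If type I error has to hold despite an override, all n = 24 designs drop out at 5.35%, 25 becomes the smallest feasible maximum, and 6/15 with success at ≥15/25 has the smallest expected size there. In that sense the design could be called minimax. The arithmetic stands, but it does not rescue the text. Section 9.3 describes a stop that terminates the study, no section gives a non-binding stop as the reason for 25, and the written cut-off is 17, not 15. A type I error limit of 3.5% would also make 6/15 with ≥15/25 minimax, but the protocol states 5%.

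A second objection is that quoting 5% for a rule with 3.4% is ordinary rounding up to the nominal level, since exact binomial designs seldom attain it. That is fair for a cut-off of 15, where 3.4% respects a 5% limit. It does not cover the written cut-off, whose power is 67.7%.

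A reader might infer that the trial should move to 10/24 because it needs fewer patients at the same power. The documents do not support that:
- The power is the same only against ≥15/25 (90.1% and 90.0%), a cut-off the protocol does not contain.
- The maximum falls by one patient.
- The expected saving under the null, 18.9 − 15.1 = 3.8 patients, assumes that accrual pauses for the interim look, whereas 9.3 continues recruitment.
- The chance of stopping early at a true 70% rises from 1.5% to 4.7%.
- Type I error passes 5% if the override in 2.1 is used.
- Current accrual is not given, and moving a futility boundary after open-label responses have been seen would itself disturb the error rates.

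**Conclusion.** The plan is wrong as written on two linked points. First, for the inputs in 9.3 and a binding stop, 15/25 is not the minimax design. Taken alone this is a labelling error worth one patient in maximum size. Second, and of more weight, the stated 5% and 90% do not belong to the rule of ≤6/15 and ≥17/25, which has 0.43% and 67.7%. At a true response rate of 70% the written rule would miss an active regimen 32.3% of the time (100 − 67.7), against at most 10% as stated.

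This should not be read as an inflated false-positive rate, because the written rule is stricter than claimed. Nor do the documents show that 15 was the intended cut-off: it is the only one that fits the stated limits, but 2.1 and 9.3 both say 17. The figures assume independent binomial responses and 25 patients counted; the minimax result also assumes a binding stop.

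**What to change.** Keep the 15/25 structure and make these wording changes together:

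1. Delete the word minimax in 2.1 and 9.1, and describe a Simon-type two-stage design with stage sizes 15 and 10.
2. Make the cut-off and error rates agree in 2.1 and 9.3. Either set success at 15 or more of 25 with type I error 3.4% and power 90.0%, or keep 17 or more and restate 0.43% and 67.7%. The sponsor should say which was intended and, if responses have already been seen, record when and why the choice was made.
3. Reconcile 2.1 with 9.3 on what happens at 6 or fewer responses, and say whether the stop is binding. Type I error is 3.4% either way with a cut-off of 15, and 0.43% either way with 17.

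The cost is a text amendment with no added patients. Keeping 17 carries the price of openly lower power; changing to 15 raises the type I error from 0.43% to 3.4%, still inside the stated 5%.
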